Screening visit(s). Screening procedures may be scheduled across more than 1 day to meet participant schedules. Prior to completing any study-related screening, participants will review and sign an informed consent form with a trained staff member. Participants will be given the opportunity to do an in-person or a remote consent. For participants that complete the remote consent, some screening procedures will also be completed remotely, including interviews and questionnaires. Participants who complete this initial eligibility screening will complete the remainder of their screening visit in person. During the screening visit, participants will be assessed for inclusion and exclusion criteria. A urine drug-screen will be collected to assess for recent drug exposure and pregnancy (when indicated), the Mini-International Neuropsychiatric Interview (M.I.N.I.), the Addiction Severity Index (McLellan, Cacciola, & Zanis, 1997), the Columbia Suicide Severity Rating Scale, a demographic questionnaire, and a health form assessing current conditions and medications will be used to help evaluate participant eligibility.

Baseline/Randomization visit. Following determination of eligibility, participants will be randomized (stratified by gender) to receive 20mg of SUVO (the maximum FDA approved dose) or placebo. Randomization will occur prior to visit 1. At the randomization visit, participants will provide a urine sample that will be tested for recent drug use and complete self-report measures as described below. They may also complete a cue-induced craving paradigm, a probabilistic reward task, and the Trier Social Stress Test (TSST) described below. Participants will also be provided with an actigraph-like device to wear for the duration of their study participation to assess sleep.

Medication dispensing will begin during the baseline session. Participants will receive a blister package with 7-days of medication dispensed as two capsules (10mg SUVO or placebo) so that medication doses can be reduced to 50% of the dose if requested by a

Date: 09/19/2024

Principal Investigator: [name].

Application Number: IRB00341328

participant. Participants will also receive a 3-day blister package as a contingency strategy in case of missed visits. Participants will be instructed to return blister packages once weekly as a measure of medication compliance.

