Weekly visits. Participants will complete visits twice weekly during the study period. At these visits, participants will be asked to complete a urine drug screen and self-report measures as described below. Medication will be dispensed once weekly during these visits.

Final/Exit visit. The final study visit will be collected at day 28-30 (+7 days) or the final day of study participation. At their final visit, participants will complete a urine drug screen and self-report measures, and tasks. Participants will be able to request SUVO prescriptions from their provider if desired and all participants can request study drug unblinding after data collection is closed.

Follow-up phone visit: Participants will be contacted via phone after the final/exit visit. Information will be collected on their experience during the study, any changes in symptoms following study exit, treatment plans going forward, and other feedback regarding the study.

Sleep diaries: To facilitate scoring of actigraphy data, participants will be asked to complete nightly sleep diaries.

The following study Measures may be used:

- Mini-International Neuropsychiatric Interview (M.I.N.I.): The MINI is a semi-structured interview that will be used to assess presence of stimulant use disorder.
- Addiction Severity Index: The ASI will be used to collect information related to severity of recent substance use disorder
- Columbia Suicide Severity Rating Scale: The C-SSRS is the standard for assessing present risk for suicidality. It will be administered at screening and end of study, and point prevalence during the study as indicated.
- Demographic questionnaire. This will ask participants basic demographic information (e.g., gender, age, race, ethnicity, employment status, etc.)
- Medical History: A self-reported medical history will be collected to determine eligibility for suvorexant administration.
- Assessment of previous medication administration: Participants will be asked whether they have ever received a number of different medications, either illicitly or through a prescription.
- Medication expectancy questionnaire. Participants will be asked to rate how much they expect to like the study drug, as well as how much they expect the study drug to help improve various symptoms (i.e., opioid use, cocaine use, sleep, stress).

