- Hypothetical purchase tasks: Participants will complete several questions asking how much they would purchase of various substances at various prices.
- Hypothetical Monetary Choice: Participants will ask whether they would hypothetically prefer a smaller amount of money at a shorter time interval, or a larger amount of money after a delay.
- Blood pressure, heart rate, and weight
- Opioid/cocaine cued choice: A paradigm in which participants will be shown two images (cues: one cocaine or opioid and one control image) presented side-by-side followed by concurrent monetary offers below each image.
- Time since last methadone or buprenorphine dose.
- Time Line Follow Back: Participants will be asked to identify “anchor events” in the time period assessed, and will then be prompted to report on their substance use, using anchor events as a guide.
- Urine Drug Screen: Qualitative tests will be used to assess evidence of recent exposure to illicit substances such as opioids, cocaine, methamphetamine, benzodiazepines, fentanyl, and cannabis. Tests will also confirm presence of buprenorphine or methadone.
- STOP-BANG questionnaire will be used as a screening measure for sleep apnea.

Date: 09/19/2024

Principal Investigator: [name].

Application Number: IRB00341328

b. If your study involves data/biospecimens from participants enrolled under other research studies with a written consent or under a waiver of consent, please list the IRB application numbers for those studies. Please note: Certificate of Confidentiality (CoC) protections applied to the data in source studies funded by NIH or CDC will extend to this new study if the funding was active in 2016. If this situation applies, Section 36, question 6 in the application will need to be answered “Yes” and “Hopkins Faculty” should be selected in question 7. No other documents are required.

N/A

c. Study duration and number of study visits required of research participants.

Participants will complete 9-10 visits (10 visits if a screening visit is broken into two visits for participant convenience) across a period of approximately 5-6 weeks: a screening visit(s), a baseline/randomization visit and 8 twice weekly visits between the 28-30 days of SUVO administration. The estimated study duration is 1 year.

d. Blinding, including justification for blinding or not blinding the trial, if applicable.

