Participants will be blinded to whether they received SUVO vs. placebo. This is meant to enhance study rigor and control for expectancy effects.

e. Justification of why participants will not receive routine care or will have current therapy stopped.

There is no current routine care for stimulant use disorder. Participants will not be removed from routine care and will continue participating in their treatment for OUD as indicated.

f. Justification for inclusion of a placebo or non-treatment group.

Inclusion of a placebo group will be necessary to determine if SUVO is efficacious in improving outcomes for patients receiving treatment for OUD and using cocaine.

g. Definition of treatment failure or participant removal criteria.

Participants will be removed from the study if they opt out or if the medical team determines it is not safe to continue in the study or if they request to discharge from the study. Participants who become pregnant, are incarcerated or hospitalized for ≥ 7 days, end their OUD treatment, or rescind consent/ask to be discharged will be removed from the study. Additional stopping rules will include not abiding by study policies and procedures, or engaging in behaviors towards staff or other participants that are abusive. Finally, development of an intercurrent illness or condition that changes the participant's risk profile may result in a medically-related discharge from the study.

Date: 09/19/2024

Principal Investigator: [name].

Application Number: IRB00341328

h. Description of what happens to participants receiving therapy when study ends or if a participant's participation in the study ends prematurely.

Participants will continue to receive their clinically-indicated care for OUD treatment.

Participants will be able to request a suvorexant prescription from their PCP if interested in continuing with the study medication after study completion.

i. If biological materials are involved, please describe all the experimental procedures and analyses in which they will be used.

Urine drug screens will be used as an outcome in this analysis. Urine drug screens will be taken at each visit using biochemical urine panel dip stick tests. The research coordinator will record the result of the urine drug screen. Urine specimens will be stored for future research.

5. Inclusion/Exclusion Criteria

Inclusion criteria:

- 1) Ages 18-65,
- 2) Meet DSM-5 criteria for stimulant use disorder,

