Suvorexant is a Schedule IV dual orexin receptor antagonist (DORA) that is FDA-approved for the treatment of insomnia. Suvorexant is 82% bioavailable and has a Tmax of 2 hours. Tmax can be delayed by food though this does not impact the Cmax. It is extensively metabolized by the liver through CYP3A enzymes. The elimination half-life is 12 hours, and it is excreted through both renal (23% unchanged) and fecal (66%) means. Suvorexant is contraindicated with other CNS depressants and alcohol and strong CYP3A inhibitors. It is rated pregnancy category C, indicating insufficient data available to make determination for human subjects. Suvorexant is contraindicated in patients with narcolepsy, patients with recent suicidal behavior, or patients with severe hepatic impairment. There is no evidence of potential overdose and a toxic dose has not been established. Clinical trials that administered up to 240mg of suvorexant reported no overdose effects, though there was a dose-dependent increase in the frequency and duration of next day somnolence. As per product label, most common side effects are sleepiness/drowsiness (7% of people), headache (7%), dizziness (3%), diarrhea (2%), dry mouth (2%), upper respiratory infection (2%), abnormal dreams (2%), and cough (2%). Serious adverse effects include sleep paralysis (7%), somnolence (7%), and worsening of depression or suicidal ideation.

b. Steps taken to minimize the risks.

Individuals with medical or psychiatric contraindications and/or individuals who are taking exclusionary medications (including CNS depressants such as benzodiazepines or other sleep medications), individuals with co-occurring moderate or severe substance use disorder, those with current and major psychiatric illness (e.g., bipolar disorder) or past 30-day suicidal behaviors are excluded for participating. Participants will be provided the maximum FDA-approved dose (20mg). All medication will be dispensed in two (10mg) capsules and participants will be informed they can refuse reduce from 2 to 1 capsule or stop taking medication at any point and we will track participant acceptance (e.g., in terms of adherence with dosing schedule) of the medication as part of the study. Given that suvorexant can cause next-day drowsiness, participants will be explicitly instructed not to drive or operate heavy machinery under any circumstances within 8 hours of taking suvorexant for the first time, or if they continue to feel

Date: 09/19/2024

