Important adverse events that are unanticipated, including pregnancy, will be reported to the Johns Hopkins IRB within 10 working days. If the important adverse events requires changes to the protocol or consent form, the PI will make those changes promptly and submit the revised documents to the IRB and appropriate other agencies.

d. Legal risks such as the risks that would be associated with breach of confidentiality.

We will minimize risk of breach of confidentiality by de-identifying data stored in the master data set. Information about study subjects will be kept confidential and managed according to the requirements of the Health Insurance Portability and Accountability Act of 1996 (HIPAA). Consistent with these regulations a signed authorization will be obtained that informs each subject of the following:

- What protected health information (PHI) will be collected from subjects in this study

Date: 09/19/2024

Principal Investigator: [name].

Application Number: IRB00341328

- Who will have access to that information and why
- Who will use or disclose that information
- The rights of a research subject to revoke their authorization for use of their PHI.

In the event that a subject revokes authorization to collect or use PHI, the investigator, by regulation, retains the ability to use all information collected prior to the revocation of subject authorization. For subjects that have revoked authorization to collect or use PHI, attempts should be made to obtain permission to collect at least vital status (i.e. that the subject is alive) at the end of their scheduled study period.

- e. Financial risks to the participants.

Participants are unlikely to incur financial risks.

9. Benefits

- a. Description of the probable benefits for the participant and for society.

The present study will help inform treatment opioid/stimulant co-use, a growing problem in our society.

10. Payment and Remuneration

- a. Detail compensation for participants including possible total compensation, proposed bonus, and any proposed reductions or penalties for not completing the protocol.

Compensation: Participants will earn \$35 for screening and \$40-75 for additional visits (payment varies based on study tasks required), and \$10 for completing the phone exit visit, for a total maximum earning potential of \$445.

11. Costs

- a. Detail costs of study procedure(s) or drug (s) or substance(s) to participants and identify who will pay for them.

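### Pregnancy is an exclusion, a removal event and a reportable event, but the protocol states a pregnancy test only at screening, so later detection rests on participant report

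*Combined protocol and SAP*

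**What the plan says.** **Testing.** Under Screening visit(s) in section 4a: "A urine drug-screen will be collected to assess for recent drug exposure and pregnancy (when indicated". The condition in brackets is not defined there or elsewhere. At the Baseline/Randomization visit, where the first pack is dispensed, "participants will provide a urine sample that will be tested for recent drug use". At the weekly visits "participants will be asked to complete a urine drug screen and self-report measures as described below", and at the final visit "participants will complete a urine drug screen and self-report measures, and tasks". The measures list in 4a describes the screen itself: "Qualitative tests will be used to assess evidence of recent exposure to illicit substances such as opioids, cocaine, methamphetamine, benzodiazepines, fentanyl, and cannabis", plus confirmation of methadone or buprenorphine.

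**Rules that need a pregnancy to be known.** Section 5 excludes pregnant participants (exclusion 2). Section 4g begins its list of removals with "Participants who become pregnant, are incarcerated or hospitalized". Section 8c sets a limit of 10 working days for telling the IRB about "Important adverse events that are unanticipated, including pregnancy". Section 8a puts the drug in pregnancy category C, "indicating insufficient data available to make determination for human subjects".

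**Mitigations.** Inclusion criterion 5 requires contraception where appropriate. Section 7b has adverse events assessed at every visit. Section 8b gives participants a number to call, and 4a adds a phone contact after exit that asks about changes in symptoms.

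**The concern.** The plan sets out what must happen when a participant becomes pregnant but schedules nothing after screening that would reveal it. Screening may be spread over more than one day, and dispensing starts at a separate later visit with no repeat test stated. A pregnancy too early to show at screening, or one that begins during treatment, would come to light only if the participant recognised it and said so. Exposure that 4g is meant to end could then continue, and the time limit in 8c could start late or after the participant has left the study. This is a matter of safety monitoring. It does not bear on the primary analysis.

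**Working it through.** The plan gives no figure to reproduce here, so the check is an inventory of the text with some simple arithmetic.

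**1. Urine collections against stated pregnancy tests**

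| Visit (section 4a) | Urine collected | Stated purpose | Pregnancy test stated |
|---|---|---|---|
| Screening | yes | drug exposure; pregnancy if indicated | yes, conditional |
| Baseline/Randomization (dispensing starts) | yes | recent drug use | no |
| Twice-weekly visits | yes | drug screen | no |
| Final/Exit | yes | drug screen | no |

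The other mentions of pregnancy (section 5, 4g, 8a, 8c) set rules or describe risk. None describes a test.

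**2. Samples per participant after screening.** Section 4c supports two counts.
- From its visit total: 9 visits − 1 screening visit = 8, or 10 visits − 2 screening visits = 8.
- From its itemised list: 1 baseline + 8 twice-weekly visits = 9.

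So there are 8 or 9 samples, taking the exit visit as the last of the twice-weekly visits. The number with a stated pregnancy test is 0 on either count.

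**3. Length of possible undetected exposure.** Dosing lasts 28-30 days.
- Conception before or at the first dose: up to the full 28-30 days.
- Conception on treatment day d: at most 30 − d days. For d = 14 that is 30 − 14 = 16 days.

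No interval from screening to first dose is stated. Section 4c gives about 5-6 weeks in total. Subtracting dosing gives 35 − 30 = 5 to 42 − 28 = 14 days. The exit visit may fall up to 7 days late, and 35 − (30 + 7) is below zero, so the lower end could be about zero. The usable statement is roughly 0 to 14 days.

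**4. Illustration of frequency (assumed inputs, none in the documents).** Suppose n = 10 to 20 of the 40 participants could become pregnant, each with probability p = 0.5% to 3% over the course.
- Expected number = n × p: 10 × 0.005 = 0.05 to 20 × 0.03 = 0.6.
- Chance of at least one = 1 − (1 − p)^n: 1 − 0.995^10 = 4.9% to 1 − 0.97^20 = 45.6%.
- Active arm only, with equal allocation assumed (n = 5 to 10): 1 − 0.995^5 = 2.5% to 1 − 0.97^10 = 26.3%.

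The range is wide because the inputs are guesses. The finding does not rest on it.

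**The case against.** The strongest reply is that this is a silence and not a contradiction. The rules in 4g and 8c operate once staff learn of a pregnancy, and neither promises surveillance. Incarceration and leaving OUD treatment sit in the same removal list without a scheduled check. The plan also has real mitigations: a contraception criterion, a screening test, adverse event assessment at every visit and a contact number. The trial is a 40-person pilot with 28-30 days of dosing, so few pregnancies are to be expected.

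Much of this stands. The sections do not contradict each other, contraception lowers the risk, and staff assess participants at scheduled visits. But contraception detects nothing, and no check on it during treatment is stated. Adverse event assessment and the contact number both depend on what the participant knows and reports, and an early pregnancy may be unknown to her. The comparison with incarceration is also limited, because here a test could be run on urine the trial already collects.

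A second reply is that staff may test anyway. A reader might infer from the text that no later urine is tested for pregnancy in practice. The documents do not support that. They show only that no test is stated. The panel description is open-ended, and it omits pregnancy even though the screening urine is tested for it, so the omission cannot settle what later screens cover. Consent pages are not in the text reviewed and might say more.

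**Conclusion.** The point holds as a gap in the stated procedures. After a conditional screening test with an undefined condition, no pregnancy test is stated for any of the 8 or 9 later urine samples, including the one taken when dispensing begins. Followed as written, the removal and reporting rules depend on participant report.

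A reader might go further and conclude that a pregnancy would be exposed for the whole course, or that the reporting limit would never start to run. The documents do not support either as the expected outcome. Full exposure is the worst case: it needs conception by about the first dose, assignment to active drug and no recognition or report for 28-30 days. Conception later in treatment means a shorter exposure.

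The number of participants who could become pregnant is not given, so no expected count can be taken from the documents. Power, the primary outcomes and their interpretation are not materially affected. The change is still worth making, because the existing safety rules lack a scheduled trigger and supplying one is cheap.

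**What to change.** Reconcile the testing text in 4a (screening, baseline, weekly and exit visits, and the urine screen entry in the measures list) with the exclusion in section 5, the removal rule in 4g and the reporting rule in 8c. Two additions would do it:

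1. Define for whom the pregnancy test is indicated.
2. State at which visits after screening, including the baseline visit where dispensing begins, urine already collected will also be tested for pregnancy.

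The exact schedule and the handling of a positive result are clinical decisions for the investigators and the IRB, and this review proposes neither.

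The cost is a few test strips per relevant participant on urine in hand, amendment wording and the occasional false positive that needs confirming. The sample size and the analysis plan need no change.

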Study Overview: Participants who are in methadone or buprenorphine treatment for OUD and are using cocaine will be recruited from the community to visit the clinic twice weekly and provide urine tests that will be analyzed for evidence of recent drug use and complete self-reported measures. All participants will be randomized to receive double-blinded doses of suvorexant (20mg, oral, QD) or placebo, which will be dispensed in blister packages for 28-30 days. Medication will be over-encapsulated and will include either 10mg SUVO or placebo. Participants will be expected to take 2 capsules each night and will be informed they can reduce their dose to 1 capsule per night if desired (these data will be documented as a secondary outcome).

Recruitment: Participants will be recruited from the community using social media advertisements, flyers, and newspaper advertisements. Recruitment will also include review of clinical records of individuals who are not clinical patients of the PI or co-investigators prior to their consent at Man Alive. At ATS, recruitment will include referral of individuals specifically for research purposes by treating clinicians not on the study team and recruitment of individuals who are patients of the study co-investigators. Interested individuals will complete a brief screening to determine initial eligibility before completing a full eligibility screen.

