Application Number: IRB00341328

is asleep, 2) wake after sleep onset (WASO), or the total number of minutes that an individual is awake after sleep onset and prior to awakening, and 3) subjective sleep quality.

Co-occurring affective symptoms. Participants will be assessed for positive and negative affect using the PANAS. Participants will report perceived stress using the Perceived Stress Scale (PSS) is a 10-item measure of perceived stress. Items are rated on a five-point scale.

Abuse Liability Assessments (i.e., Medication Satisfaction Questionnaire). Participants will be asked to complete abuse liability measures. Participants will also be assessed for adverse events and serious adverse events in each visits. The abuse liability of the blinded study drug will be assessed by asking participants to rate “drug effects”, “good effects”, and “bad effects”, on a 0-100 point VAS, with 0 being “None” and 100 being “Extremely”. Participants will also report the perceived street value of the study drug. These subjective drug effect ratings are considered by the FDA to be the gold standard for assessing abuse liability.

Adverse events We will follow standard FDA guidelines regarding adverse events. Participants will be able to self-report adverse events via a study contact number. Events will be documented on a standardized form that adheres to FDA standards for adverse event reporting (e.g., event, system affected, start and stop date/time, perceived relationship to the study, severity, expectedness).

c. Statistical plan including sample size justification and interim data analysis.

Primary Aim 1. To examine whether SUVO 20mg reduces opioid and cocaine use and craving relative to placebo, a series of mixed models will be conducted. For analyses with a binary outcome (i.e., use at each assessment), generalized logistic models will be used, and for analyses with a continuous outcome (i.e., craving), linear mixed models will be used. Mixed effects models will also be used to compare drug cue reactivity at baseline and during the final week. For each model, we will include main effects of timepoint and medication group, as well as an interaction term. If the two treatment groups are systematically different on demographic or use characteristics at baseline, these measures will be included as covariates in the analysis. Models will involve a random intercept.

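### The exit-visit window runs up to 7 days past the dosing period, so the single post-baseline point of the cue-reactivity contrast can be measured off drug

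*Combined protocol and SAP*

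**What the plan says.** Treatment length is set in section 4a, Study Overview: capsules are given double-blind, "which will be dispensed in blister packages for 28-30 days". Under Weekly visits, "Medication will be dispensed once weekly during these visits". The Baseline/Randomization paragraph adds a reserve: "Participants will also receive a 3-day blister package as a contingency strategy in case of missed visits". It does not say whether the reserve is replaced once used, or whether it may be taken after day 28-30.

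The Final/Exit visit paragraph sets the timing: "The final study visit will be collected at day 28-30 (+7 days) or the final day of study participation". On content it says: "At their final visit, participants will complete a urine drug screen and self-report measures, and tasks".

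Section 7a lists cue reactivity, rated on visual analogue scales in the presence of drug cues, among the primary outcomes. Section 7c says mixed models will "compare drug cue reactivity at baseline and during the final week". The Visual Analog Ratings entry in 4a schedules the cue-exposed ratings only at unspecified timepoints.

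Section 4c describes the schedule as screening, "a baseline/randomization visit and 8 twice weekly visits between the 28-30 days of SUVO administration". Section 8a gives the pharmacokinetics: "The elimination half-life is 12 hours".

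No section ties the final assessments to the date of the last capsule, or says how a late exit visit is to be analysed.

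**The concern.** The cue-reactivity contrast is meant to show what the drug does at the end of treatment. It has one post-baseline period, so each participant's whole contribution after baseline rests on when that assessment takes place. A window that extends only forward lets the assessment move past the end of supply, to a time when a drug with a 12-hour half-life has essentially gone. If the effect fades with the drug, off-drug values pull the difference between arms toward zero, and the loss is proportional to the share of values affected. With 40 participants in total there is little power to spare. The stress and reward tasks done at the exit visit are exposed in the same way.

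Without a pre-stated rule, the handling of late values would also be chosen after the data are in.

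**Working it through.** **No stated power to reproduce.** Section 7c gives a sample size of 40, two-tailed tests and alpha 0.05, and refers to a moderate-to-strong effect. It gives no numerical effect size, SD or power, so the figures below are illustrations. They assume 20 per arm and a two-sample t-test on a single endpoint.

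**Step 1: the gap.** The end of the course and the end of the window move together:
- 28-day course: latest visit day 28 + 7 = 35; gap 35 − 28 = 7 days.
- 30-day course: latest visit day 30 + 7 = 37; gap 37 − 30 = 7 days.
- If a full, unused 3-day pack is taken after the course: 7 − 3 = 4 days.

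These are the gaps at the end of the window. A visit one to three days late has a shorter gap, possibly none if the reserve is in use.

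**Step 2: drug remaining.** Fraction left = 2^(−hours/12).
- 4 days: 96/12 = 8 half-lives; 2^−8 = 0.0039, about 0.4%.
- 7 days: 168/12 = 14 half-lives; 2^−14 = 0.00006, about 0.006%.

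On either reading, a visit at the end of the window is effectively off drug.

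**Step 3: cue reactivity, one post-baseline point.** Let f be the share of final values taken off drug and L the share of the effect lost off drug. The effect retained is 1 − f × L. Neither f nor L is in the documents. The effect giving 80% power at 20 per arm is d = 0.91 (0.909 before rounding).

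| f | Full loss (L = 1): d | Power | Half persists (L = 0.5): d | Power |
|---|---|---|---|---|
| 0 | 0.91 | 80% | 0.91 | 80% |
| 10% | 0.82 | 71% | 0.86 | 76% |
| 20% | 0.73 | 61% | 0.82 | 71% |
| 30% | 0.64 | 50% | 0.77 | 66% |
| 40% | 0.55 | 39% | 0.73 | 61% |

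At smaller true effects the starting point is already lower. With every value on drug, power is 69% at d = 0.8 and 34% at d = 0.5. With 25% off drug and full loss, these become 46% and 21%.

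**Step 4: urine, about 8 repeated screens.** If only the last of 8 screens can be off drug, the averaged effect retained is 1 − f × L/8. With full loss:
- f = 20%: 1 − 0.2/8 = 97.5% retained; illustrative power at d = 0.91 goes from 80% to 78%.
- f = 100%: 1 − 1/8 = 87.5% retained, so the loss cannot exceed 12.5%.

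Section 7a also averages the craving scales over visits, so the same reasoning applies.

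One caveat: section 7c does not say how time is coded or which term is tested. If the test were a linear time-by-group slope over baseline and 8 visits, the last screen would carry more leverage. With f = 25% and full loss, the slope keeps 87% (effect growing linearly) or 75% (effect constant from the first post-baseline visit).

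**Step 5: the visit schedule.** The visits listed in 4c sum to 1 + 1 + 8 = 10, or 2 + 1 + 8 = 11 with split screening. The stated total is 9-10. Section 4c puts the 8 visits inside the dosing period, while 4a allows the final one after it. The reader cannot tell whether the exit visit is the eighth visit or an additional one.

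**The case against.** The case for leaving the plan alone has five parts.

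- **The cue rating may be on drug.** Ratings occur at unspecified timepoints, the final week of 7c could be met by an on-drug visit, and 4c places the visits within dosing. A reader might infer that the exit visit is the only post-baseline cue measure. The documents do not say so. What stands is narrower: the planned contrast has one post-baseline period, the tasks are assigned to the exit visit, and nothing keeps that visit inside dosing.
- **The gap is usually shorter.** A reader might pair a day-37 visit with a day-28 last dose and infer 9 days, but that mixes two course lengths. Seven days is the limit relative to the nominal course, and many late visits would fall well short of it.
- **Urine is robust.** A reader might infer that a late last screen weakens the urine outcome as it does cue reactivity. The outcome is recorded at every screen, so an averaged effect is barely touched. This objection holds, apart from the slope case.
- **Full loss is the worst case.** The documents give no persistence figure, and the mechanism proposed in section 6a, restored dopaminergic functioning, need not reverse at once. This holds, and is why the half-persistence column is shown.
- **Dropping late values could do harm.** Lateness arises after randomisation and may relate to drug use or arm. Excluding 20% of values (16 per arm) gives 70% power at d = 0.91, against 71% for keeping them with half the effect persisting. This holds, so exclusion belongs only in a sensitivity analysis.

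**Conclusion.** The concern holds for cue reactivity and the other tasks done at the exit visit. The stated window permits these to be collected up to 7 days after the course, or about 4 if an unused reserve pack is taken, and no other provision prevents it. If 20% of values are affected, assumed power of 80% becomes 61% to 71%, depending on whether all or half of the effect is lost. This rests on equal allocation, a single-endpoint t-test, d = 0.91, and assumed values for the late fraction and persistence.

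It does not extend in any serious way to the urine and craving outcomes as averaged over visits. Nor does it show that the plan intends an off-drug measurement, or that the sample size of 40 is wrong. This is a cheap improvement to a pilot study, not a flaw that undermines its main comparison. The visit count is a separate matter of consistency and adds nothing to the dilution argument.

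**What to change.** 1. In 4a, schedule the end-of-treatment task battery at the last twice-weekly visit within the 28-30 day dosing period, with a window that opens early rather than running late. Keep the +7 days as a fallback, and for the exit and safety contact.
2. Record days since the last dose for each final assessment, using the blister packs that participants already return weekly.
3. In 7c, keep every randomised participant's value in the primary contrast, including late ones. Pre-specify a sensitivity analysis that excludes assessments made after the last dose.
4. In 7c, state how time is coded and which model term is tested, since this decides how much weight the last visit carries.
5. Reconcile 4a and 4c on the length of supply, the reserve pack, the timing of the final visit and the number of visits.

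The cost is a short wording amendment to 4a, 4c and 7c, with no new procedures and no change to dosing. The downside is that some participants will be assessed after slightly fewer days of treatment.
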